7.9. Blinding

The study is non-blinded.

7.10. Follow-up Visits

Patients will report to the office at the specified intervals below. Under the guidance of the Investigative team at each visit, SJM field representatives may assist with programming of the patient's device as needed during the course of the study.

Missed visits and visits that occur outside of the specified time windows will be documented as protocol deviations.

7.10.1. 6 Week Visit

Patients will complete additional follow-up visits at 6 weeks for continued monitoring of the safety and efficacy of the therapy. All programming data will be captured on the appropriate case report form.

A map of paresthesia coverage is collected along with programming parameters, lead impedance, and device data. Any changes in medications will be recorded.

Pain metrics to be collected are patient reported pain relief, NRS, and SF-MPQ. Quality of Life (EQ-5D) will also be assessed.

7.10.2. 24 Week Visit

Patients will complete additional follow-up visits at 24 weeks for continued monitoring of the safety and efficacy of the therapy. All programming data will be captured on the appropriate case report form.

A map of paresthesia coverage is collected along with final programming parameters, lead impedance, and device data. Any changes in medications will be recorded.

Pain metrics to be collected are patient-reported pain relief, NRS, and SF-MPQ. Quality of Life (EQ-5D) will also be assessed.

7.10.3. Unscheduled Visit

An Unscheduled Visit form will be used if a patient makes an unscheduled office visit. The Healthcare Utilization (HCOR) form will be completed for all unscheduled visits.

The primary reason for the visit determines the need for additional information. In the event of a device malfunction, the changes in device will be captured on the Product Out of Service form. In the event of an adverse event, the investigator should complete the Adverse Event form. If the patient needs to be reprogrammed, the Paresthesia Location and Programming forms. If a revision or replacement is required, then the Additional Surgery and Product Out of Service forms will be completed.

7.11. Outcome Measures

7.11.1. Characterization of Procedure Time

Procedure time will be characterized along the following metrics

- Total operating room time (from prep to recovery)
- Skin-to-skin surgery time (from first incision to last suture)
- Programming time (time while delivering test stimulation to address proper lead placement)
- Fluoroscopy time

7.11.2. Adverse Events

Adverse events will be collected according to the section below. Outcomes will be in percentage of patients experiencing events and total number of events, and will be stratified by severity, type, and resolution.

7.11.3. Coverage

As described below, paresthesia coverage of painful regions will be measured by comparing pain maps to paresthesia maps. Adequate coverage of painful regions with paresthesia and avoidance of paresthesia outside of painful regions will be assessed.

7.12. Additional Data

The Study Coordinator or designee will give the patient the questionnaires to complete on his or her own. It is important that the patient understands the meaning of all the words in the questionnaires. The patient should be instructed to ask any questions about the questionnaires if further explanation is needed. Once the patient has completed the questionnaire, the Study Coordinator or designee will review the questionnaire for completeness to verify that all questions have been answered and only one response is chosen for each item.

Short-Form McGill Pain Questionnaire (SF-MPQ-2) (Dworkin et al., 2009)

The Short-Form McGill Pain Questionnaire version 2 (SF-MPQ-2) is a widely used scale used to measure the major symptoms of both neuropathic and non-neuropathic pain. The self-administered questionnaire consists of a set of 22 different pain descriptors. The patient is instructed to indicate how accurately the applicable the descriptor word describes their pain on a scale ranging from 0 ('None') to 10 ('Worst Possible'). The questionnaire takes approximately 5-10 minutes to complete. There are a total of 3 sensory subscales (continuous pain descriptors, intermittent pain descriptors, and predominantly neuropathic pain descriptors) and 1 affective subscale scores. The total SF-MPQ-2 score is the sum of the four subscale scores. Higher scores indicate a higher severity of symptoms.

Pain Evaluation Form

Patients will be provided with a questionnaire to complete at follow-up visits. Patients will evaluate their pain relief from the device and rate their current, average, worst, and least pain.

EuroQol (EQ-5D) generic health index questionnaire (Hurst, Kind, & Ruta, 1997)

EQ-5D is a standardized instrument for measuring health outcome. Applicable to a wide range of health conditions and treatments, it provides a simple descriptive profiles and single index value for health status. The EQ-5D has standard layout for the five-dimensional (mobility, self-care, usual activities, pain/discomfort, anxiety/depression) descriptive system for recording an individual's current EQ-5D self-reported health state. Each of the five dimensions will be answered by one of five responses of increasing severity (no problems/slight problems/moderate problems/severe problems/unable or extreme) within a particular EQ-5D dimension.

Pain Location Form

The Pain Location Form includes a map of the body that is labeled with different numbered regions. The patient is instructed to shade in or place an X in the area the patient is feeling pain.

Paresthesia Coverage Form

The Paresthesia Coverage Form includes a map of the body that is labeled with different numbered regions. The patient is instructed to shade in or place an X the area the patient is feeling stimulation/paresthesia. Patients will also indicate which area(s) of pain relief has given them the greatest improvement over their daily activities. This form looks similar to the Pain Location Form so it should be made clear to the patient that one is for pain and one is for paresthesia.

8. Adverse Events (AEs)

Adverse events are solicited at every study visit throughout the duration of the study. Adverse events will also be solicited at any unscheduled visits that occur.

8.1. AE Definitions

An ADVERSE EVENT is “Any change, undesired, noxious or pathological in a patient or patient illustrated by signs, symptoms and /or laboratory changes that occur during a clinical study, whether or not considered drug/treatment related.”

A SERIOUS ADVERSE EVENT (SAE) is where the event is/causes:

- Life threatening or fatal
- Requires hospitalization \geq 24 hours or prolongs an existing hospitalization
- The patient to be disabled
- Congenital anomaly or birth defect

A NON-SERIOUS ADVERSE EVENT is an event other than one described above.

A DEVICE-RELATED ADVERSE EVENT is an event where the Investigator feels that the device (i.e. IPG, lead, external device) contributed in any way to the adverse event occurring.

A PROCEDURE-RELATED ADVERSE EVENT is one that the Investigator feels that the implant procedure (i.e. permanent or revision) contributed in any way to the adverse event occurring within 30 days post-procedure.

As defined in 21 CFR §812.3 an UNANTICIPATED ADVERSE DEVICE EFFECT (UADE) is “any serious adverse effect on health or safety or any life-threatening problem or death caused by, or associated with a device, if that effect, problem, or death was not previously identified in nature, severity, or degree of incidence in the investigational plan or application (including a supplementary plan or application), or any other unanticipated serious problem associated with a device that relates to the rights, safety, or welfare of patients.” An adverse device event that is not listed in Section 8.4 or included in the labeling for the device could potentially be classified as a UADE. If an UADE occurs, the investigator must notify St. Jude Medical Technical Services immediately, but no later than 10 working days after the investigator first learns of the effect, or in accordance with IRB policies.

A LIFE-THREATENING ADVERSE EVENT is one that places the patient, in the view of the initial reporter, at immediate risk of death from the adverse event as it occurred, i.e., it does not include an event that, had it occurred in a more severe form, might have caused death.

DISABILITY is defined as a substantial disruption of a person's ability to conduct normal life functions, as assessed by the patient and the Investigator.

A TREATMENT EMERGENT ADVERSE EVENT includes an event that was not present during the Baseline Evaluation and that occurred or worsened during treatment.

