3.1. Design

This is a post-market, prospective, multicenter, parallel designed, non-randomized, non-blinded, 6-month study. A minimum of 50 patients will be implanted from up to 4 active sites, coordinated by a single lead investigator.

Patients who have had a successful SCS trial and are indicated for permanent implantation will be approached to participate in this study prior to permanent implantation. Patients will be recruited and enrolled by physicians at any one of the involved sites. Each Investigator will only use one method (awake or non-awake) according to his/her typical practice. Patients will receive treatment from their enrolling physician.

[figure not shown]

Table 1: Study Schedule

Timing of visit	Activities at visit	Case Report Forms
Screening and Informed Consent (may be immediately after Trial System Explant)	Patient evaluated for eligibility Patient signs informed consent Schedule patient for baseline evaluation at treatment site	Enrollment Form Inclusion/Exclusion Criteria Form
Baseline Evaluation 7-28 days after screening	Patient completes questionnaires Complete history and physical exam Record current medication use Collect patient reported data	Baseline Self Evaluation Form Pain Location Form Pain Evaluation Form SF-MPQ-2 (Pain Quality) EQ-5D (Quality of life) Medication Form
Permanent System Implantation	Permanent system implantation Record any complications Record any changes in medication Discourage activation at discharge Save digital recording or EMG recording if system permits.	Surgery Form Adverse Event Form Programming Form (if programmed at discharge) Medication Form
Initial Programming Visit	Record any complications Record any changes in medication Provide patient with the patient programmer and charging system Record patient's global impression of satisfaction with the implant procedure.	Programming Form Paresthesia Coverage Form Patient Global Impression Form Medication Form
6 weeks 42 ± 7 days after activation	Record any complications Record any changes in medication Patient completes questionnaires Modify programming parameters (if necessary) Collect patient reported data	Follow-up Visit Form Pain Evaluation Form Pain Location Form Programming Form SF-MPQ-2 (Pain Quality) EQ-5D (Quality of life) Paresthesia Coverage Form Medication Form

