7.8. Device Activation

The permanent system device activation visit will occur approximately 2-3 weeks after permanent system implantation. At this visit, each patient will have their device programmed to comparable individualized programming parameters. All patients will receive a Patient Programmer that will enable him/her to activate the ON and OFF positions and adjust amplitude within the prescribed range.

A map of paresthesia coverage is collected along with final programmed parameters, lead impedance, and device data. Any changes in medications are noted as well.

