8.2. AE Recording

All device and/or procedure-related Adverse Events volunteered by the patients or elicited by the Investigator must be recorded on the AE forms provided. All serious AEs must be recorded whether or not considered device or procedure- related.

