8.5.2. Relationship to Device/Procedure

An adverse event where the causal relationship to the device and/or procedure has been classified as *possibly*, *probably*, or *definitely*, the relationship must meet the NIH definition for relatedness of an adverse event to an intervention as follows:

- *Possibly* Device/Procedure-Related: (must meet at least 2 criteria)
 - 1) Has a reasonable temporal relationship to intervention,
 - 2) Could not readily have been produced by the patient's clinical state,
 - 3) Could not readily have been due to environment or other interventions,
 - 4) Follows a known pattern of response to intervention.
- *Probably* Device/Procedure -Related: (must meet at least 3 criteria)
 - 1) Has reasonable temporal relationship to intervention,
 - 2) Could not readily have been produced by the patient's clinical state or have been due to environmental or other interventions,
 - 3) Follows a known pattern of response to intervention,
 - 4) Disappears or decreases with reduction in dose or cessation of intervention.
- *Definitely* Device/Procedure -Related: (must meet all 4 criteria)
 - 1) Has a reasonable temporal relationship to intervention,
 - 2) Could not readily have been produced by the patient's clinical state or have been due to environmental or other interventions,
 - 3) Follows a known pattern of response to intervention,
 - 4) Disappears or decreases with reduction in dose or cessation of interventional and recurs with re-exposure.

9. Data Review and Database Management

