10.1. Statistical Plan

The study design for this investigation is a post-market, prospective, multicenter, parallel design, non-blinded study with primary analysis at 24 weeks. The primary objective in this study is to demonstrate the effectiveness and safety of the non-awake procedure compared to the awake procedure.

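### Section 8.1 stops counting procedure-related adverse events at 30 days, in conflict with 8.5.2, so late non-serious harm blamed only on the surgery goes unrecorded in a primary outcome analysed at 24 weeks

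*Combined protocol and SAP*

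**What the plan says.** Section 2.3 makes the number and type of adverse events a primary variable. Section 10.1 describes a "non-blinded study with primary analysis at 24 weeks". Section 10.3.2 compares the percentage of patients with an adverse event between arms. It names neither the class of event nor the period over which events count.

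Four rules decide which events reach the adverse event form:

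- **Section 8.1, procedure-related:** the investigator feels that the implant procedure, whether permanent implant or revision, "contributed in any way to the adverse event occurring within 30 days post-procedure".
- **Section 8.1, device-related:** this "is an event where the Investigator feels that the device (i.e. IPG, lead, external device) contributed in any way to the adverse event occurring". There is no day limit.
- **Sections 8.2 and 8.3, recording:** "All device and/or procedure-related Adverse Events volunteered by the patients or elicited by the Investigator must be recorded on the AE forms provided". Serious events are recorded whatever their cause. Section 8.3 says that events related to neither device nor procedure are not recorded, unless they are serious.
- **Section 8.5.2, grading:** one scale (possibly, probably, definitely) covers device and procedure together. Its only timing criterion is "Has a reasonable temporal relationship to intervention", with no number of days.

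**The concern.** The trial compares two ways of performing the same implant, so harm from the procedure is central to the safety question. The definition in 8.1 acts as a filter on recording and not only as a label. Once a late non-serious event fails the 30-day test and is not also blamed on the device, the plan gives no instruction to write it down, and no later analysis can recover it. A primary safety comparison described as a 24-week analysis would then hold only 30 days of data for this one class of event.

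The conflict with 8.5.2 adds a risk of bias. Sections 3.1 and 6 tie each investigator and each site to one method, and Section 7.9 says that the study is not blinded. If sites in one arm apply the 8.1 limit and sites in the other apply 8.5.2, the difference in recording practice is inseparable from the difference between methods.

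**Working it through.** The plan states no figure to reproduce on this point. The check is to follow one type of event through the rules and then show how large the loss could be under stated assumptions.

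**Step 1. Which late events are recorded?** Take an event that starts after day 30 from the latest implant or revision procedure.

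| Event with onset after day 30 | Rule | Recorded? |
|---|---|---|
| Serious, any cause | 8.2, 8.3 | Yes |
| Non-serious, device contributed | 8.1 device definition, 8.2 | Yes |
| Leads to a revision | Separate primary metric, 10.3.3 | Counted there, no day limit |
| Non-serious, attributed to the procedure only | 8.1 procedure definition, 8.3 | No under 8.1; possibly yes under 8.5.2 |

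Only the last row is lost, and it is also the row on which the two sections disagree.

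**Step 2. How far apart are 8.1 and 8.5.2?** Under 8.5.2 a grade of possibly related needs any two of four criteria. The timing criterion need not be one of them. Even at the grade of definitely related, where all four are needed, timing has only to be reasonable. An event first arising on day 40 could therefore be graded possibly procedure-related under 8.5.2 while failing the definition in 8.1. Nothing in the plan says which section prevails.

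**Step 3. What could the loss be?** The documents give no rate for late, non-serious, procedure-only events, so the following rates are assumptions for illustration.

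- *e* = proportion of patients with an event that is recorded anyway: assumed 10% to 20%.
- *l* = proportion with a late procedure-only event, independent of the first: assumed 2% to 10%.
- Patients per arm: 25, from the minimum of 50 enrolled 1:1 (10.2).

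Rate with all events counted = 1 − (1 − e)(1 − l). Understatement = that rate − e = (1 − e) × l.

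| e | l | All events counted | Recorded | Understatement | Patients per 25 |
|---|---|---|---|---|---|
| 10% | 2% | 11.8% | 10% | 1.8 points | 0.45 |
| 10% | 10% | 19.0% | 10% | 9.0 points | 2.25 |
| 20% | 2% | 21.6% | 20% | 1.6 points | 0.40 |
| 20% | 10% | 28.0% | 20% | 8.0 points | 2.00 |

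If both arms follow 8.1, both rates fall. If one arm follows 8.1 and the other 8.5.2, with identical true rates and every late event accepted as related under 8.5.2, the understatement column becomes a spurious difference between arms of 1.6 to 9.0 percentage points.

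**The case against.** The strongest reply is that very little escapes. The device definition asks only whether the hardware contributed in any way. Several harms listed in 8.4 sit at or below the implant: seroma at the generator site, persistent pain at the electrode or generator site, and numbness or weakness below the implant level. An investigator could readily see a device contribution in these. Disabling events are serious and always recorded. Revisions are counted separately, and a revision opens a new 30-day window. Section 8.3 also speaks of recording related events throughout the study, and a site relying on 8.5.2 could record a late event anyway.

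Most of this stands, and it limits the point to the narrow class in Step 1. It does not remove the point. Whether a late event enters then depends on an unblinded investigator assigning it to the device. That label also affects the breakdown by type planned in 7.11.2. That a site could follow 8.5.2 instead confirms the conflict.

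Three stronger readings are tempting, and the documents do not support them.

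- **That the visit schedule causes the loss.** Activation is about 2-3 weeks after implantation (7.8) and the 6-week visit is "42 ± 7 days after activation", so it falls no earlier than day 14 + 35 = 49. But the limit concerns when an event occurs. An event on day 20 can be recorded at that visit, and Section 8 solicits events at every visit, including initial programming.
- **That the share of follow-up lying beyond day 30 measures the loss.** It is a share of calendar time and not of events. Device-related and serious events are covered for the whole period.
- **That the window is too short for a badly placed lead to show itself under stimulation.** The lead is part of the device, so a lead-position problem can be recorded as device-related at any time.

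**Conclusion.** The point holds in a limited form. Read as written, 8.1 together with 8.3 discards non-serious events that start after day 30 and are attributed to the procedure alone. Section 8.5.2 contradicts that limit. The affected outcome is primary, is analysed at 24 weeks, and concerns the intervention being compared.

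The size cannot be established from the documents. Under the assumed rates above, the loss is 0.4 to 2.25 patients per 25-patient arm, and a lower true rate would make it smaller. A reader might infer that the 24-week adverse event rate is certainly understated, or that the arms are certainly affected differently. Neither follows. The first needs such events to occur, and the second needs sites to read the sections differently or the true rates of these events to differ between arms. What is certain is that the plan permits both. The correction is worth making because it is cheap and the lost data cannot be recovered afterwards.

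**What to change.** 1. In Section 8.1, delete the 30-day limit from the procedure-related definition for study recording. Relatedness is then judged by the 8.5.2 criteria, for onset at any time up to the 24-week visit.
2. In Section 10.3.2, state that the adverse event rate counts all recorded events through 24 weeks. Changing 8.1 alone would leave this open.
3. Make sure that the adverse event form captures onset date. The form is not included in the document, so the field may already exist.
4. Report events with onset within 30 days of the procedure as a descriptive subgroup, which keeps the perioperative summary.

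The cost is one definition, one sentence in the analysis section and, at most, one form field. The downside is a few more late and weakly related events to adjudicate, and a slightly higher reported rate.

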8.2. AE Recording

All device and/or procedure-related Adverse Events volunteered by the patients or elicited by the Investigator must be recorded on the AE forms provided. All serious AEs must be recorded whether or not considered device or procedure- related.

8.3. Reporting AEs

Throughout the course of the proposed study, all device and/or procedure-related adverse events will be recorded and monitored by the Investigator(s) at each participating site. Additionally, any serious adverse events observed by the investigator or reported by the patients, whether or not ascribed to the device or procedure will be recorded. Non-device/procedure-related adverse events including but not limited to common cold, other bodily pain (such as dental or neck pain) or elective outpatient surgery with hospitalization less than 24 hours will not be recorded.

Only adverse events that occur during or after system implantation will be collected. Every effort will be made to remain alert to possible adverse experiences and unexpected findings. If adverse experiences occur, the first concern will be the safety of the patient and appropriate medical intervention will be made.

Individual reports of device and/or procedure-related adverse events and all serious adverse events should be documented and reported appropriately on the adverse event case report form. An investigator shall submit to the IRB a report of any unanticipated adverse effect (UADE) occurring during the investigation as soon as possible, in accordance with IRB policies.

The Investigator must report all SAEs (e.g. unanticipated death or serious injury require hospitalization greater than 24 hours) to the IRB as soon as possible, in accordance with IRB policies. This notification can occur by email, telephone, or fax and the site will forward the completed AE form as soon as it is available.

The Investigator must also promptly report the resolution to all reported serious, unanticipated, or device/procedure-related AEs. Non-serious adverse events should be reported at the next routine contact.

All AEs shall also be reported to SJM and reviewed on a monthly basis. All SAEs will be submitted to the FDA by SJM immediately upon receipt. All AEs will be reviewed on a quarterly basis by SJM per their own standard operating procedures.

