3.2. Justification for study given risks/benefit outcome

Spinal Cord Stimulation is a commercially available neurostimulation therapy available for treatment of chronic intractable pain of the trunk and/or limbs to patients today. Traditionally, SCS leads are placed in the epidural space while the patient is awake and able to give direct feedback in order to ensure adequate paresthesia coverage. Using EMG for lead implantation will allow the patient to be placed under general anesthesia and to be potentially more comfortable than during the awake procedure. The purpose of the proposed clinical study is to collect data necessary to make a direct comparison between the awake procedure and the non-awake procedure using EMG.

The Investigator will review the subject's medical record to ensure that the subject complies with all inclusion/exclusion criteria. The target population consists of subjects indicated for a neurostimulation system. The present study will permit the physician to adhere to their standard of care for continued medication usage or any current treatment methods prior to enrollment.

The risks and benefits are the same for these two lead placement techniques since the implant procedure is the same. No additional adverse events from non-awake placement are anticipated. Considering the severity of chronic pain and its debilitating effect on patients' lives, spinal cord stimulation provides an alternative means of pain reduction with minimal risk for subjects who have exhausted other options.

4. Study Devices

All study devices are in commercial distribution in the United States and Europe as an aid in the management of chronic intractable pain of the trunk and/or limbs. St. Jude Medical (SJM) received FDA approval for the Eon Mini IPG system under the PMA P010032/S32 and Eon IPG system under the PMA P010032/S014. The Lamitrode leads received clearance under K990469 (standard), K053250 (90 and 110cm), K033429 (C-Series), K022222 (S-Series), K063080 (Tripole 8C, 16C, and Exclaim), K090907 (Penta) and K991784 (extensions).

Any SJM market-cleared IPG may be used. Any SJM market-cleared paddle lead may be used. Percutaneous leads may not be used.

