10.3.2. Number of adverse events

Hypothesis:

The non-awake is comparable to the awake method in the number of adverse events.

Metrics:

Rate of adverse events (percentage of patients with an adverse event)

Statistical Tests:

Chi-square or Fisher's exact test as appropriate based on the number of adverse events
Significance at $\alpha < 0.05$, with no adjustment for the multiple comparisons

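### Non-serious adverse events are recorded only if the unblinded investigator links them to an implant procedure whose scope is undefined, so the primary adverse-event percentage depends on attribution habits nested within arm

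*Combined protocol and SAP*

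**What the plan says.** **What is recorded.** Section 8.2: "All device and/or procedure-related Adverse Events volunteered by the patients or elicited by the Investigator must be recorded on the AE forms provided". The same section has serious events recorded whatever their cause. Section 8.3 says unrelated non-serious events are not recorded, and gives examples: "Non-device/procedure-related adverse events including but not limited to common cold, other bodily pain (such as dental or neck pain". It also restricts collection to events during or after system implantation.

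**Who decides, and about what.** Section 8.1 defines a procedure-related event as "one that the Investigator feels that the implant procedure (i.e. permanent or revision) contributed in any way to the adverse event", within 30 days after the procedure. Under Section 8.5 the investigator classifies each event. Section 7.9 says the study is not blinded, and Section 3.1 says: "Each Investigator will only use one method (awake or non-awake) according to his/her typical practice". No independent adjudication is described.

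**What differs between arms.** Section 7.6.1 has the awake patient under local anaesthetic and conscious sedation. Section 7.6.2 has the non-awake patient under general anaesthesia throughout, with EMG monitoring. Section 3.2 nevertheless treats the implant procedure as identical in the two arms and adds: "No additional adverse events from non-awake placement are anticipated".

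**Where the data go.** Section 10.3.2 sets the primary hypothesis as "The non-awake is comparable to the awake method in the number of adverse events" and the metric as "Rate of adverse events (percentage of patients with an adverse event". It does not say which adverse events count.

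**The concern.** Safety of non-awake placement is part of the primary objective (Section 2.1). The two methods differ in anaesthesia, airway handling, positioning and monitoring, so non-serious harms from these are among those the comparison should detect. They are also the harms whose link to the implant procedure is least clear under the plan's wording. Whether such an event reaches the form depends on how the investigator reads one undefined term.

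Because every investigator belongs to one arm, a difference in reading between sites becomes a difference between arms. The filter acts before the data are collected, so the planned chi-square or Fisher test cannot correct it. The hypothesis is comparability without a margin (Section 10.2), so a shrunken difference would be easy to read as support.

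**Working it through.** The point is mainly textual. The documents state no overall adverse-event rate, so there is no plan figure to reproduce. Table 2 gives only revision, repositioning and infection rates and procedure time.

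**Step 1: trace a non-serious event from patient to endpoint.**
- Section 8.1 defines an adverse event whether or not it is treatment-related.
- Sections 8.2 and 8.3 put it on the form only if it is related or serious.
- Section 10.3.2 counts patients with an adverse event, without repeating that restriction. In practice the metric is therefore the percentage with a related or serious event, and the relatedness rule determines it.

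**Step 2: does the implant procedure include what differs between arms?**
- Towards no: Section 8.1 explains the term only as permanent or revision. Section 3.2 calls the procedure the same in both arms, which cannot be so if anaesthesia and monitoring are part of it. One criterion for a possible relationship in Section 8.5.2 asks whether the event could readily be due to other interventions, and anaesthesia can be read as one. The list in Section 8.4 names no anaesthetic, airway, positioning or monitoring event. Section 8.3 does not say whether an event at induction falls during implantation.
- Towards yes: the Section 8.1 test is met by any contribution. Section 7.6 includes anaesthesia and intraoperative monitoring in preparation for the surgery. Section 6 describes the non-awake arm as implantation under general anaesthesia with EMG.

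Both readings are available, and nothing in the plan makes sites choose the same one.

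**Step 3: illustrate the size, on assumptions only.** The minimum of 50 patients enrolled 1:1 (Section 10.2) gives 25 per arm. Assume a risk *b* = 20% of an event that is always recorded, an independent risk *g* of a non-serious method-specific event, and a share *a* of the latter that is attributed and so recorded. Then:

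recorded rate = 1 − (1 − *b*)(1 − *a·g*)

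| *g* | all recorded (*a* = 1) | half (*a* = 0.5) | none (*a* = 0) | patients of 25 missed if none recorded |
|---|---|---|---|---|
| 10% | 28% | 24% | 20% | 0.08 × 25 = 2 |
| 20% | 36% | 28% | 20% | 0.16 × 25 = 4 |
| 30% | 44% | 32% | 20% | 0.24 × 25 = 6 |

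With *b* = 30%, full recording gives 37%, 44% and 51%, so 7, 14 and 21 points are lost if none is recorded.

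**Step 4: apply the filter to both arms.**
- Equal true rates, unequal attribution: with *g* = 20% in both arms, attributing all in one and half in the other records 36% against 28%, a spurious 8 points. Attributing none in the second arm records 36% against 20%, a spurious 16 points. Swapping the arms reverses the sign.
- Unequal true rates, nothing attributed: the recorded difference is 0, while the true difference is 0.8 × (*g* non-awake − *g* awake). With each *g* between 10% and 30%, this runs from −16 to +16 points. With *g* = 0 in the awake arm it is 8 to 24 points.

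**Step 5: effect on the test.** Take *g* = 0 in the awake arm and *b* = 20%. Fisher's exact test at 25 per arm then has power of 5.2%, 15% and 33.3% for *g* = 10%, 20% and 30% if all events are recorded. If half are recorded it is 3.0%, 5.2% and 9.0%, and if none are it is 2.2%, the size of the test. Power is low even with full recording, so the capture rule is not the only limit on this comparison.

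**The case against.** The strongest reply is that the text already captures these events. Dental and neck pain are not barred: they appear only as examples of events judged unrelated, and any contribution from the procedure within 30 days makes an event recordable. Section 8.5.2 asks for only two of four criteria for a possible relationship, and an event following airway management could meet two without the criterion on other interventions. Section 7.6 mentions anaesthesia as part of preparing the patient. Adverse events are solicited at every visit (Section 8), and Table 1 and Section 7.6.3 ask for complications with no relatedness condition. Serious events are recorded in any case.

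Most of this stands and limits the point. A reader might infer that the plan forbids recording dental or neck pain after general anaesthesia; it does not. Nor is Section 8.4 confined to device and lead events: it lists infection, haematoma, cerebrospinal fluid leakage and seroma and says it is not exhaustive. That dental or neck pain can follow general anaesthesia is general clinical knowledge, not something the documents state.

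The reply does not remove the ambiguity. A broad reading is permitted but not required, and Section 3.2 points the other way. The complications entries might allow some events to be recovered, but Section 10.3.2 does not use them.

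**Conclusion.** The concern holds as one of undefined scope and possible differential recording. As written, the plan lets a site omit non-serious harms specific to its method, and the primary adverse-event percentage depends on attribution habits that are fully nested within arm. That the investigator who attributes also implants is inferred from Section 3.1, where patients are treated by their enrolling physician.

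Two stronger inferences are tempting and not supported. The first is that the bias favours non-awake placement. The same filter applies to sedation and local-anaesthetic harms in the awake arm, and Section 1 itself describes the awake operation as stressful and liable to patient movement, so the net direction is unknown. The second is that 2 to 6 of 25 non-awake patients would be wrongly counted as event-free. That range rests on an assumed 20% base rate, an assumed 10% to 30% method-specific risk and no attribution at all. It shows what the rule could do and is not an estimate.

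**What to change.** - **Section 8.1:** state that the procedure includes anaesthesia or sedation, airway management, positioning and neuromonitoring, in both arms.
- **Sections 8.2 and 8.3:** record every adverse event from operating-room entry to 30 days after implantation regardless of attribution, and classify relatedness afterwards. Limit the dental and neck pain exclusion to events outside that window.
- **Section 10.3.2:** say that the metric is the percentage of patients with a related or serious event through 24 weeks, under the widened definition. Report the 30-day all-cause percentage by arm beside it as a supportive analysis.
- **Section 3.2:** reconcile the statement that the procedure and its risks are the same with the revised Section 8.1.

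The 30-day all-cause rate should not replace the primary metric. Expected postoperative symptoms could push it towards saturation in both arms, and it would drop later lead and device events, although Section 10.1 places the primary analysis at 24 weeks.

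The cost is protocol wording, more adverse-event forms, more minor events, and somewhat higher reported percentages in both arms. The 30-day window and solicitation at every visit are already in the plan.
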